**Table 6-2. CRS Grading (ASTCT; Lee et al, 2019)**

CRS Parameter	Grade 1	Grade 2	Grade 3	Grade 4
Fever a	Temperature $\geq 38^{\circ}\text{C}$	Temperature $\geq 38^{\circ}\text{C}$	Temperature $\geq 38^{\circ}\text{C}$	Temperature $\geq 38^{\circ}\text{C}$

		With		
Hypotension	None	Not requiring vasopressors	Requiring a single vasopressor (not including vasopressin)	Requiring multiple vasopressors (not including vasopressin)
		And/or b		
Hypoxia	None	Requiring low-flow oxygen ( $\leq 6$ L/minute) nasal cannula or blow-by	Requiring high-flow nasal cannula ( $> 6$ L/min), facemask, non-rebreather mask, or Venturi mask	Requiring positive pressure (eg, CPAP, BiPAP, intubation and mechanical ventilation)

ASTCT = American Society for Transplantation and Cellular Therapy; BiPAP = bilevel positive airway pressure; CPAP = continuous positive airway pressure; CRS = cytokine release syndrome  
Organ toxicities associated with CRS may be graded according to CTCAE v5.0 but they do not influence CRS grading.

a Fever is defined as temperature  $\geq 38^{\circ}\text{C}$  not attributable to any other cause. In subjects who have CRS then receive antipyretic or anti-cytokine therapy such as tocilizumab or steroids, fever is no longer required to grade subsequent CRS severity. In this case, CRS grading is driven by hypotension and/or hypoxia.  
b CRS grade is determined by the more severe event: hypotension or hypoxia not attributable to any other cause. For example, a subject with temperature of  $39.5^{\circ}\text{C}$ , hypotension requiring 1 vasopressor, and hypoxia requiring low-flow nasal cannula is classified as grade 3 CRS.

#### 6.2.1.6.1.1 Neurological Dose-limiting Toxicity

The etiology of NT is unclear but has been postulated to stem from endothelial activation/microangiopathy, possibly downstream of IL-1 secretion by monocytes/macrophages (Gust et al, 2017; Giavidris et al, 2018; Norelli et al, 2018). Onset usually occurs with or after CRS (mostly CRS grade  $\geq 3$ ). Isolated NT has been described after administration of anti-PSMA T-BsAbs (Velasquez et al, 2017). Early symptoms of NT include tremor, dysgraphia, expressive aphasia, impaired attention, and lethargy; delirium, headache, agitation, cerebral edema, ataxia, confusion, seizure, and coma may subsequently develop.

If NT symptoms are suspected, grading should be performed to guide appropriate management; a consensus grading scheme published by Lee and colleagues is reproduced here and may be used to grade NT (Table 6-3; Lee et al, 2019).

**Table 6-3. American Society for Transplantation and Cellular Therapy Immune Effector Cell-associated Neurotoxicity Syndrome Consensus Grading for Adults (Lee et al, 2019)**

Neurotoxicity Domain	Grade 1	Grade 2	Grade 3	Grade 4
ICE score a	7–9	3–6	0–2	0 (subject is unarousable and unable to perform ICE)

Depressed level of consciousness b	Awakens spontaneously	Awakens to voice	Awakens only to tactile stimulus	Subject is unarousable or requires vigorous or repetitive tactile stimuli to arouse. Stupor or coma.
Seizure	NA	NA	Any clinical seizure focal or generalized that resolves rapidly or nonconvulsive seizures on EEG that resolve with intervention	Life-threatening prolonged seizure (> 5 min); or repetitive clinical or electrical seizures without return to baseline in between
Motor findings c	NA	NA	NA	Deep focal motor weakness such as hemiparesis or paraparesis
Elevated ICP/cerebral edema	NA	NA	Focal/local edema on neuroimaging d	Diffuse cerebral edema on neuroimaging; decerebrate or decorticate posturing; or cranial nerve 6 th palsy; or papilledema; or Cushing's triad

EEG = electroencephalogram; ICANS = immune effector cell-associated neurotoxicity syndrome; ICE = immune effector cell-associated encephalopathy; ICP = intracranial pressure; NA = not applicable. Note: ICANS grade is determined by the most severe event (ICE score, level of consciousness, seizure, motor findings, raised ICP/cerebral edema) not attributable to any other cause; for example, a subject with an ICE score of 3 who has a generalized seizure is classified as grade 3 ICANS.

a A subject with an ICE score of 0 may be classified as grade 3 ICANS if awake with global aphasia, but a subject with an ICE score of 0 may be classified as grade 4 ICANS if unarousable.

b Depressed level of consciousness should be attributable to no other cause (eg, no sedating medication).

c Tremors and myoclonus associated with immune effector cell therapies may be graded according to CTCAE v5.0, but they do not influence ICANS grading.

d Intracranial hemorrhage with or without associated edema is not considered a neurotoxicity feature and is excluded from ICANS grading. It may be graded according to CTCAE v5.0.

Source: Lee et al, 2019

Neurological adverse events in subjects receiving AMG 340 mandate frequent CAR-T-cell therapy associated toxicity (CARTOX-10) or immune effector cell encephalopathy (ICE) examinations ([Table 6-4](#)) and neurological exams. Early neurology consultation, use of anti-epileptics, and intensive care unit/airway support as needed are encouraged. [Table 6-5](#) provides a guideline for treatment that may be used for subject management, however, it is recommended that investigators adhere to institutional guidelines for NT management, if they exist.

**Table 6-4. Encephalopathy Assessment Tools for Grading of Immune Effector Cell-associated Neurotoxicity Syndrome (Lee et al, 2019)**

CARTOX-10	ICE
• Orientation: orientation to year, month, city, hospital, president/prime minister of country of residence: 5 points	• Orientation: orientation to year, month, city, hospital: 4 points • Naming: ability to name 3 objects (eg, point to clock, pen, button): 3 points
• Naming: ability to name 3 objects (eg, point to clock, pen, button): 3 points	• Following commands: ability to follow simply commands (eg, "Show me 2 fingers" or "Close your eyes and stick out your tongue"): 1 point
• Writing: ability to write a standard sentence (eg, Our national bird is the bald eagle): 1 point	• Writing: ability to write a standard sentence (eg, Our national bird is the bald eagle): 1 point
• Attention: ability to count backwards from 100 by 10: 1 point	• Attention: ability to count backwards from 100 by 10: 1 point

CARTOX-10 = chimeric antigen receptor toxicity; ICE = immune effector cell encephalopathy.

Note: CARTOX-10 (left column) has been updated to the ICE tool (right column). ICE adds a command following assessment in place of 1 of the CARTOX-10 orientation questions. The scoring system remains the same.

Note: Scoring: 10, no impairment; 7-9, grade 1 ICANS; 3-6, grade 2 ICANS; 0-2, grade 3 ICANS; 0 due to subject unarousable and unable to perform ICE assessment, grade 4 ICANS.

Source: Lee et al, 2019

**Table 6-5. Suggested Guidelines for Management of Neurological Toxicity**

Adverse Event Category	Guidelines
Neurologic adverse event after dosing with AMG 340	
 
Consult neurologist
 
Continue neurologic monitoring
 
Prophylactic anti-epileptic (ie, levetiracetam)
 
Consider MRI/CT, EEG, and/or LP
 
Contact Medical Monitor
 

If adverse event is grade $\geq 2$ , add	
 
Consider Corticosteroids (eg, dexamethasone 10 to 20 mg IV every 12 to 24 hours, higher doses or with more frequency, if clinically indicated)
 
Withhold AMG 340 until resolution to grade <math>\leq 1</math>.
 

If adverse event is grade $\geq 3$ , add	
 
High-dose corticosteroids (methylprednisolone 2 mg/kg loading dose followed by 2 mg/kg/day divided 4 times per day). Higher /more frequent doses if indicated. Taper when grade 1 or better)
 
Anti-epileptics for seizures/seizure-like activity
 
ICU monitoring
 
Airway protection
 
Consider continuous EEG monitoring
 

If adverse event is grade 4, add	
 
If cerebral edema/other grade 4 toxicity is rapid onset or the subjects is unresponsive to above: methylprednisolone IV 1 g/day x 3 days, followed if clinically indicated by taper.
 
Consider hyperventilation / hyperosmolar therapy for cerebral edema.
 

CT = computed tomography; EEG = electroencephalogram; ICU = intensive care unit; IV = intravenous;

LP = lumbar puncture; MRI = magnetic resonance imaging

#### **6.2.1.6.1.2 Miscellaneous Dose-limiting Toxicity**

Any toxicity thought to be related to the study drug that, at the discretion of the investigator, is thought to warrant withholding the drug. Other adverse events may be considered a DLT as determined by the Medical Monitor, in conjunction with the investigator.

All decisions regarding continued dosing for individual subjects will be medically managed by the investigator, in conjunction with the Medical Monitor(s), as appropriate. These decisions will be driven by the DLT criteria as described above.

Any subject who does not complete the full 21-day DLT observation period for any reason other than DLT will be considered non-DLT-evaluable for dose escalation and/or MTD assessment and will be replaced at the same dose level. Additional subjects may be enrolled at a given dose level in the absence of DLT to explore factors influencing adverse events or to accumulate additional safety data.

#### **6.2.2 Dosage Adjustments, Delays, Rules for Withholding or Restarting, Permanent Discontinuation**

##### **6.2.2.1 Amgen Investigational Product: AMG 340**

The reason for dose change of AMG 340 is to be recorded on each subject's CRF(s).

Subjects experiencing CRS must continue to be hospitalized as described in [Table 6-6](#) and as deemed appropriate by the investigator. Subjects should be monitored for CRS symptoms, including vital signs and pulse oximetry at least every 2 hours for 12 hours, or until CRS grade  $\leq 1$ , whichever is earlier.

Re-starting treatment after an interruption/delay due to an adverse event or if the interruption/ delay was  $> 72$  hours, regardless of the reason, should be performed under medical supervision. Dexamethasone premedication is mandatory prior to re start, and prior to re-escalation to the target dose in case of dose reduction. The following assessments should be performed as per the Schedule of Activities for cycle 1, depending on duration of hospitalization:

- vital signs, pulse oximetry
- physical examination
- neurological examination (only in case the treatment interruption was due to a neurologic event)
- weight
- ECOG
- safety labs (hematology, chemistry, coagulation, urinalysis)

The subject should be hospitalized for up to 48 hours after re-start of the infusion depending on the specific adverse event that has led to the interruption/delay (causality and severity, see [Table 6-6](#) for adverse event management and restart guidance) or tolerability prior to delay for logistical reason and as per agreement with the Amgen Medical Monitor. **Re-introduction of the step dosing may be required for long delays and should be considered on a case-by-case basis with the Amgen Medical Monitor.**

#### **6.2.2.2 Management of COVID-19 Infection**

Subjects with evidence of COVID-19 infection should be closely monitored while being treated with AMG 340. Follow the guidelines in [Table 6-6](#) for AMG 340 treatment interruption, resumption, and discontinuation due to COVID-19 infection. Subjects with active COVID-19 infection should not be dosed with AMG 340 until infection has resolved and if being treated with an anti-infective therapy, the course of such therapy should have been completed. Management of COVID-19 infection should be tailored to the appropriate prophylaxis and/or treatment according to the local standard of care and institutional guidelines.

#### **6.2.2.3 Management of Monkeypox Infection**

Subjects with evidence of Monkeypox infection should be closely monitored while being treated with AMG 340. Follow the guidelines in [Table 6-6](#) for AMG 340 treatment interruption, resumption, and discontinuation due to Monkeypox infection. Management of Monkeypox infection should be tailored to the appropriate prophylaxis and/or treatment for the Monkeypox infection according to the local standard of care and institutional guidelines.

**Table 6-6. AMG 340 Dose Modification Guidelines for Adverse Events**

Grade	Description of Severity	Interruption/Delay	Specific Management	Re-start Guidance	Permanent Discontinuation
Infusion-related Reaction					
1	Mild transient reaction; infusion interruption not indicated; intervention not indicated	N/A	Consider medication to control infusion reaction as deemed appropriate by the investigator according to local standard of care and institutional guidelines. Increase monitoring of vital signs as medically indicated until the subject is deemed medically stable.	N/A	N/A
2	Therapy or infusion interruption indicated but responds promptly to symptomatic treatment (eg, antihistamines, NSAIDs, narcotics, IV fluids); prophylactic medications indicated for $\leq$ 24 hours	Short-term infusion: Immediate interruption/delay until event has improved to grade $\leq$ 1		
 
• Re-start possible, if successfully managed and improvement to <math>\leq</math> grade 1 in <math>\leq</math> 14 days.
 
• Delay of the next infusion: 
 
– <math>\leq</math> 7 days: administer the delayed infusion (as long as the next scheduled infusion is <math>></math> 6 days from delayed infusion) and follow the schedule of assessments for the cycle day on which the infusion was originally planned.
 
– <math>></math> 7 days: skip the delayed infusion and resume schedule of assessments for the next scheduled infusion.
 
 
 
• Hospitalization: 48 hours
 
• Dose modification: resume at the same dose or reduce to next lower dose if clinically indicated
 
	If subject missed more than 2 consecutive doses of AMG 340

Page 1 of 19

Abbreviations and footnotes defined on last page of table.

**Table 6-6. AMG 340 Dose Modification Guidelines for Adverse Events**

Grade	Description of Severity	Interruption/Delay	Specific Management	Re-start Guidance	Permanent Discontinuation
Infusion-related Reaction (continued)					
3	Prolonged (eg, not rapidly responsive to symptomatic medication and/or brief interruption of infusion); recurrence of symptoms following initial improvement; hospitalization indicated for clinical sequelae	Immediate interruption/delay until event has improved to grade $\leq 1$	Consider supportive therapy including steroids as clinically indicated.  Increase monitoring of vital signs as medically indicated until the subject is deemed medically stable.	
 
As for grade 2 infusion-related reaction, with the exception of mandatory dose modification: reduce to next lower dose
 
	If subject missed more than 2 consecutive doses of AMG 340
4	Life-threatening consequences; urgent intervention indicated	N/A	As for grade 3 infusion-related reaction	N/A	Immediately stop the infusion (if applicable) and permanently discontinue AMG 340 (monotherapy or in combination with pembrolizumab) therapy

Abbreviations and footnotes defined on last page of table.

Page 2 of 19

Table 6-6. AMG 340 Dose Modification Guidelines for Adverse Events

Grade	Description of Severity	Interruption/ Delay	Specific Management	Re-start guidance	Permanent Discontinuation
Neurologic Events					
≤ 2	For CRS-related neurological events, use ICANS grading and management system (Section 6.2.1.6.1.1)	Interrupt AMG 340 until the event improves to grade ≤ 1	Follow institutional guidelines for management	Resume AMG 340 no less than 72 hours after the initial observation of the grade 1 or 2 adverse event.	N/A
3			Administer corticosteroids per local practice	Resume AMG 340 no less than 7 days after the initial observation of the grade 3 adverse event. Reduce AMG 340 by 1 dose level.	
 
Initial grade 3 neurologic event does not improve to grade ≤ 1 within 7 days, OR
 
Grade 3 neurologic event reoccurs at the lower dose level within 7 days of re-initiation
 

4		--	--	--	Permanently discontinue AMG 340
Seizure		Interrupt AMG 340 until the event improves to grade ≤ 1	Administer corticosteroids and anti-seizure medication per local practice	
 
Refer to grade 3 neurologic events above for dose level rules for re-instituting infusion.
 
Do not re-initiate AMG 340 until 7 days after the last seizure and after therapeutic levels of anti-seizure medication are likely to have been achieved.
 
	If a second seizure occurs with re-initiation of AMG 340 at any dose

Page 3 of 19

Abbreviations and footnotes defined on last page of table.

Table 6-6. AMG 340 Dose Modification Guidelines for Adverse Events

Grade	Description of Severity a	Interruption/Delay	Specific Management	Restart Guidance	Permanent Discontinuation
Cytokine Release Syndrome (see Section 6.2.1.6 for additional guidance and grading scale details)					
1	Symptoms are not life-threatening and require symptomatic treatment only 
 
• Feverb: <math>\geq 38^{\circ}\text{C}</math>
 
• Hypotension: none
 
• Hypoxia: none
 
	No action required	
Administer:
 
 
• Symptomatic treatment (eg, paracetamol/acetaminophen) for fever
 
 
Monitor:
 
 
• CRS symptoms including temperature, blood pressure, and pulse oximetry
 
• Fluid status, maintain IVF as needed
 
• Consider Chest X-Ray and obtaining appropriate cultures to rule out infection
 
 
For subjects with rapid onset (< 4 hours from start of infusion), extensive co-morbidities or poor performance status, strong suggestion to manage per grade 3 CRS guidance below.
 
Thrombocytopenia occurring in the setting of CRS can be managed per Section 6.2.1.4 and/or per institutional guidelines.
	N/A	N/A

Page 4 of 19

Abbreviations and footnotes defined on last page of table.

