##### **6.2.1.4 Toxicity Management**

For the purpose of medical management, all adverse events and laboratory abnormalities that occur during the study must be evaluated by the investigator. The table of clinical toxicity grades from the NCI-CTCAE, Version 5.0 (available on CTEP home page: <http://ctep.info.nih.gov>) is to be used in the grading of adverse events and laboratory abnormalities that are reported as adverse events, each of which will be followed to satisfactory clinical resolution, except for CRS and NT which will be graded according to Lee et al (2019). AMG 340 has not been tested clinically in humans, so the adverse event profile in humans is not known.

Adverse events should be classified as pre-existing or as treatment-emergent adverse events:

- A treatment-emergent adverse event is defined as an adverse event not present prior to initiation of AMG 340 treatment, or an adverse event present prior to AMG 340 initiation that worsens in intensity and/or frequency after initiation of AMG 340 treatment.
- A pre-existing adverse event is an adverse event that does not meet these criteria. Subjects with pre-existing adverse events should be assessed for any underlying illness or other causes and treated as appropriate.

Subjects with treatment-emergent adverse events should also be assessed for intercurrent illness or other causes and treated as appropriate. If a treatment-emergent adverse event is unequivocally due to a subject's underlying malignancy or other extraneous cause, dosing with AMG 340 may be modified at the discretion of the Principal Investigator, following discussion with the Medical Monitors. If a treatment-emergent adverse event is not unequivocally due to the subject's underlying malignancy or other extraneous cause, regardless of whether there is a 'reasonable possibility' that the treatment-emergent adverse event is AMG 340-related, the dose of AMG 340 should be modified as follows:

- For subjects who have completed cycle 1 and have at least clinically or radiographically stable disease (SD, MR, PR or CR) but have experienced a reversible treatment-emergent adverse event, the dose of study drug can be delayed for up to 14 days after the scheduled dosing date. A subject for whom dosing is delayed > 14 days should be discontinued from the study.

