- During any cycle, if a subject develops an ANC < 500/ $\mu$ L, platelets < 10,000/ $\mu$ L, or a hemoglobin < 6.5 g/dL, blood samples must be collected every 3 days and study treatment withheld. Treatment may resume when ANC returns to  $\geq$  1,000/ $\mu$ L, platelet counts return to  $\geq$  50,000/ $\mu$ L or baseline platelet count levels (in subjects with baseline platelets < 50,000/ $\mu$ L), or hemoglobin returns to  $\geq$  8.0 g/dL.
- AMG 340 should be discontinued in any subject who experiences CRS, TLS, or a non-hematologic treatment-emergent adverse event that meets DLT equivalent criteria until resolution of the toxicity to  $\leq$  grade 1 or baseline; thereafter study drug may be resumed with one dose level reduction with Medical Monitor approval.

Up to 2 dose reductions are allowed to manage toxicity; thereafter toxicity will be deemed 'unacceptable' and the subject will be discontinued from therapy. Assessment schedules and cycles are fixed and should continue regardless of whether a dose is held.

While investigator discretion should be used for subject management with regards to toxicities, guidelines for management of CRS and NT are provided in [Table 6-6](#) and [Table 6-5](#).

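### A first grade 4 seizure falls under two rows of Table 6-6 with opposite instructions, permanent stop and conditional restart, and nothing says which row governs

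*Protocol*

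**What the plan says.** Under Neurologic Events, Table 6-6 has rows for grade 2 or lower, grade 3 and grade 4, and then a row headed Seizure where a grade would normally stand.

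- **Grade 4 row:** the only instruction is to "permanently discontinue AMG 340". The interruption, management and restart cells hold dashes.
- **Seizure row:** drug is held until the event is grade 1 or lower, with corticosteroids and anti-seizure medication. On dose, the row says "Refer to grade 3 neurologic events above for dose level rules for re-instituting infusion", which means one dose level lower. On timing, drug is withheld "until 7 days after the last seizure and after therapeutic levels of anti-seizure medication are likely to have been achieved". Permanent discontinuation applies "If a second seizure occurs with re-initiation of AMG 340 at any dose".

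Table 6-3 (Section 6.2.1.6.1.1) defines a grade 4 seizure as "Life-threatening prolonged seizure (> 5 min); or repetitive clinical or electrical seizures without return to baseline in between". Section 6.2.1.4 puts neurotoxicity on that consensus scale: CTCAE applies "except for CRS and NT which will be graded according to" the ASTCT consensus publication.

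Section 6.2.1.4 also has a general rule: "AMG 340 should be discontinued in any subject who experiences CRS, TLS, or a non-hematologic treatment-emergent adverse event that meets DLT equivalent criteria" until the event has resolved, and "thereafter study drug may be resumed with one dose level reduction with Medical Monitor approval".

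**The concern.** A seizure can be grade 4 the first time it happens. Read literally, one row then forbids any further AMG 340 and the next row sets out how to restart it. The general rule in Section 6.2.1.4 leans towards restart, because it permits resumption after a DLT-equivalent non-hematologic event without setting aside the events for which Table 6-6 requires a permanent stop.

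At stake is whether a subject is re-exposed to a first-in-human T-cell engager after a life-threatening neurologic event. Two sites could treat the same event differently and both be following the protocol. The choice also feeds the exposure summaries and the table of adverse events leading to withdrawal of AMG 340 (SAP Section 9.6.2).

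**Working it through.** The plan states no figure to reproduce. The check compares the texts and then runs one dated example.

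**Step 1. Which grades can a seizure have?** In Table 6-3 the seizure domain is not applicable at grades 1 and 2. On this scale a seizure by itself is therefore grade 3 or grade 4, the two grades that Table 6-6 handles in opposite ways.

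**Step 2. Apply both rows to a first seizure.**

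| First seizure | Graded row | Seizure row | Compatible? |
|---|---|---|---|
| Grade 3 | Hold; restart one level lower, no sooner than 7 days after onset | Hold; restart one level lower, no sooner than 7 days after the last seizure | Yes |
| Grade 4 | Permanent stop | Hold; conditional restart one level lower; permanent stop only on a second seizure | No |

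**Step 3. Look for a rule that ranks the rows.**

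- Section 6.2.1.4, resumption sentence: no grade 4 exception. Its closing pointer to Tables 6-5 and 6-6 for CRS and neurotoxicity guidance sets no precedence.
- Table 6-5, grade 4: adds treatment and says nothing about discontinuation.
- Section 6.2.1.6.1.2: says who decides on continued dosing and ties decisions to the DLT criteria. Those criteria (Section 6.2.1.4.1.1) do not separate grade 3 from grade 4 for an event of this kind.
- Table 6-6, footnote f: allows departures by written agreement, but is marked only on the Monkeypox and COVID-19 parts of the table.

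None of these settles the matter.

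**Step 4. Does the Section 6.2.1.4 sentence conflict elsewhere?** It also names CRS and TLS. Table 6-6 requires permanent discontinuation for grade 4 CRS and for grade 3 or higher clinical TLS. If the DLT-equivalent condition is read as applying to all three kinds of event, the conflict still holds at grade 4, because grade 4 CRS and grade 4 TLS are DLTs under Section 6.2.1.4.1.2.

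**Step 5. Dated example.** Take a first grade 4 event whose last seizure is on cycle 1 day 2.

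- *Q3W without step dosing.* Cycle 2 day 1 is day 1 + 21 = 22, and 22 − 2 = 20 days after the last seizure, beyond the 7-day minimum. The dose is on schedule, so the 14-day delay limit is not engaged. The Seizure row allows the dose one level lower if the event is grade 1 or lower, anti-seizure levels are likely therapeutic and the Medical Monitor approves. The grade 4 row forbids it.
- *With step doses on days 5 and 8.* The 7-day wait runs to day 2 + 7 = 9, so even the Seizure row blocks both doses as scheduled. A later full dose needs Medical Monitor approval under Section 6.2.1.2. The grade 4 row forbids that dose too.

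**Step 6. Effect on escalation.** A grade 4 seizure in the DLT window is a non-hematologic event of grade 3 or higher and is not among the listed exceptions. It counts as a DLT whichever row governs treatment afterwards.

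**The case against.** The rows can be read together. The Seizure row borrows its dose rule from grade 3, so it may be meant for grade 3 seizures, with the grade 4 row as an absolute stop. Grade 4 infusion reactions and grade 4 CRS are also permanent stops in Table 6-6, so a cautious reader would stop. That is probably the intent. It remains an inference: a reader could as reasonably hold that a row written specifically for seizures overrides the general grade row.

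Restart is also not automatic. Section 6.2.1.4 requires Medical Monitor approval, and Section 6.2.2.1 requires medical supervision and dexamethasone premedication. An unsupervised restart is therefore unlikely. But approval is a decision step and does not say which rule the Medical Monitor should apply. As written, Section 6.2.1.4 allows approval of what the grade 4 row forbids.

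The CRS and TLS conflict is strictly a separate matter, general text against table. It is included because the same sentence causes it and the same clause cures it; it does not add weight to the seizure point. The objection that the effect is small in frequency and absent from dose escalation is correct.

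**Conclusion.** The concern holds. For a first grade 4 seizure the protocol gives two incompatible instructions and no order of precedence. This is a conflict between stated safety rules and should be corrected, although the likely intent is clear.

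Its size is rare but all-or-nothing for the subject affected. No seizure rate is given and none is assumed. Section 2.2.4.3 lists no seizure among the 23 subjects treated by 08 March 2022, although 9 of them had CRS and Table 2-2 names seizure among its possible signs. The effect on the withdrawal table would be at most an occasional entry. DLT counts, sample size and error rates are untouched.

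The conclusion rests on reading the grade 4 row as covering every grade 4 neurologic event, seizures included, and on the Table 6-3 definition of a grade 4 seizure.

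**What to change.** In Table 6-6, relabel the row *Seizure, grade ≤ 3* and add: *A grade 4 seizure follows the grade 4 row: permanently discontinue AMG 340.* In Section 6.2.1.4, add to the resumption sentence: *except where Table 6-6 requires permanent discontinuation.* That clause also resolves the grade 4 CRS and grade 3 or higher TLS conflicts.

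The cost is one label, one sentence and one clause in the next amendment, plus a notice to sites. No procedures or data are added. The clinical downside is that no subject could restart after a grade 4 seizure, even one who was benefiting, but the grade 4 row already says this. If the sponsor wants the opposite rule, it should exempt seizures from the grade 4 row explicitly and justify the exemption.
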